4 STUDY PLAN

4.1 Study Design

This is a non-randomized, prospective, open-label implementation study to determine the feasibility of establishing and integrating a PGx test into clinical care. The effectiveness aims will be assessed by comparing toxicity outcomes using a historical control group without clinical genotyping. The implementation will be deployed across cancer care sites within Penn medicine in sequential fashion, starting with PCAM followed by PPMC, and LGH.

Patients with a GI malignancy initiating chemotherapy with a fluoropyrimidine (5-FU or capecitabine) and/or irinotecan will be consented to undergo *DYPD* and *UGT1A1* genotyping, the study intervention. The PGx test order will be placed by the research coordinator and signed by the medical oncologist; a blood sample will be obtained by the phlebotomist, or saliva self-collected by the patient in clinic, and sent to CAG for genotyping. Results will be returned in the Precision Medicine tab in PennChart. For patients with an actionable genotype (variants that would require a dose adjustment of 5-FU, capecitabine or irinotecan), clinical decision support (CDS) tools will alert the ordering oncologist of the PGx result and the recommended dose adjustment. The prescribing oncologist will ultimately decide the chemotherapy dose incorporating clinical and genetic factors. The efficacy and safety of this PGx-guided approach will be determined by comparing the incidence of severe treatment related adverse events to a historical control group of GI cancer patients enrolled into PMBB.

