7.5 Data collection at each chemotherapy infusion (time 0 to 6 cycles)

The following information will be assessed at each chemotherapy visit by study personnel or extracted from the medical record with each chemotherapy treatment during the first six cycles if performed as part of usual care and available in the medical record.

- Routine physical examination: height (cm), weight (kg), calculated body mass index (BMI)
- Vital signs: heart rate, blood pressure
- Hematology: hemoglobin, hematocrit, white blood cell count, ANC, neutrophils, eosinophils, basophils, lymphocytes, monocytes, platelets prior to treatment
- Clinical chemistry: sodium, potassium, calcium, glucose, creatinine, BUN, AST, ALT, alkaline phosphatase, total bilirubin, albumin
- Creatinine clearance (using Cockcroft-Gault formula)
- Concomitant medications (including start date, dose, unit, frequency, route of administration and indication)
- Chemotherapy course: dates of treatment, dose of each treatment for first 6 cycles
- Adverse events: date of reported treatment-related symptoms, date of emergency department (ED) visits and/or hospitalizations (if applicable), clinical course and symptom duration, ED/hospitalization medical billing information. Severe TRAEs are defined as those requiring treatment in the hospital, ED, or Oncology Evaluation Center (OEC).
- Serial questionnaires assessing patient reported outcomes (PROs) for symptoms associated with adverse events will be prospectively collected by the study team at the time of each treatment for the first 6 cycles (see data collection tool in Appendix 14.6)

The following information will be extracted from the medical records and/or tumor registry at the 6-month (\pm 2 months) follow-up period if performed as part of usual care and recorded in the medical record.

- Overall patient survival (duration of patient survival from time of treatment initiation)
- Progression free survival (time from treatment initiation until disease progression or worsening)
- Information regarding tumor response from computed tomography (CT) scans will also be collected as available. This is expected to be classified by the treating oncologist as complete response (CR), partial response (PR), stable disease (SD), or progressive

disease (PD) per response evaluation criteria in solid tumors (RECIST) guideline version 1.1.

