8 STATISTICAL PLAN

8.1 Sample size

For the implementation aims, the sample size is based on average GI oncology clinical volume and anticipated number of patients that are eligible for testing. We anticipated testing 500-800 patients during the course of the study at the three Penn Medicine sites. No hypothesis testing will be performed.

For the effectiveness aims, we hypothesize that the chemotherapy-related severe TRAEs will decrease from 60% in the variant carriers receiving full dose chemotherapy in the historical control group enrolled into the PMBB to 30% in variant carriers receiving genotype guided chemotherapy.¹⁸ The following table presents the power for different sample sizes per group and different expected proportions experiencing severe TRAEs in the PGx group, based on two-sided Fisher's exact test at the alpha level of 0.05 (Table 5). Based on the frequencies of *DPYD* and/or *UGT1A1* in the population (~10%), testing 500 patients in each group will result in ~50 patients with actionable genotypes.

Table 5. Power estimate for the reduction in Severe TRAEs with PGx testing

Toxicity rate	39% in PGx	35% in PGx	30% in PGx
N in each group with actionable variants			
18	17.8%	24.8%	35.6%
36	32.3%	45.8%	63.6%
48			80%
54	49.4%	66.3%	83.9%
70		80%	
72	67.4%	82.9%	
97	80%		

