Analysis methods	27	
1. Primary outcome: We will report the number and proportion of tests returned prior to the first dose of chemotherapy in the prospective testing arm only as this outcome was not relevant for the historical control group. The proportions were compared among clinical sites using a chi-square test. The test turn-around time was reported as median (interquartile range) and compared using the Wilcoxon rank-sum test.
 
2. Secondary outcomes:
 
 a. Fidelity- proportion of dose modifications made in agreement with the genotype guided dosing recommendations at the first dose was reported, no hypothesis testing was performed. b. Penetrance- proportion of tests orders divided by the number of patients eligible for testing based on pharmacy records indicating the number of fluoropyrimidine prescriptions during the enrollment time frame, no hypothesis testing was performed. c. Treatment-related adverse events (TRAЕ): proportion of patients experiencing a severe treatment related adverse event defined as those requiring hospitalization, visit to the emergency department, or visit to the oncology evaluation center (OEC). The proportion of patients with severe TRAEs in the prospective cohort were compared between the DPYD variant carriers vs DPYD wild-type patients. The proportion of patients with TRAEs were compared between the prospective and historical control groups among DPYD variant carriers. The proportion of patients with TRAEs in the prospective cohort were compared between the UGT1A1 poor metabolizers vs UGT1A1 normal and intermediate metabolizers. The

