		
proportion of patients with TRAEs were compared between the prospective and historical control groups among UGT1A1 poor metabolizers. Chi-square tests were used for all comparisons. Factors contributing to having a TRAE were evaluated using a multivariable logistic regression model adjusting for age, sex, race, tumor type, ECOG score, presence of metastases, intent of treatment, DPYD phenotype, and UGT1A1 phenotype using a stepwise approach.
 
 d. Relative dose intensity for fluoropyrimidines and irinotecan, defined as cumulative dose administered divided by the anticipated cumulative dose over six cycles reported as mg/m² was compared between variant carriers and wild-type patients (or PM vs. IM/NM for irinotecan) in the prospective cohort using t-tests. Relative dose intensity for fluoropyrimidines and irinotecan, was compared between the prospective and historical control groups in variant carriers (or PM for irinotecan) using t-tests. e. Patient reported outcomes (PROs) during the first six cycles of chemotherapy were compared in the prospective cohort between DPYD variant carriers and wild-type patients using chi-square tests in the subset that completed PROs. f. Patient knowledge and attitudes towards PGx testing were evaluated using chi-square and t-tests as appropriate.
Missing data	28	
 a. Prospective completion of chemotherapy related toxicity per the National Cancer Institute-Common Terminology Criteria for Adverse Events (NCI-CTCAE) was not feasible due to a lack of a consistent research coordinator throughout the study. In addition, the completion rate for the PROs was very low therefore we could not assign a grade to the adverse event. b. Revised definition severe toxicities from \geq Grade 3 toxicities to treatment related adverse events requiring treatment in the hospital, emergency department, or oncology evaluation center.

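### The prospective versus PMBB carrier contrasts ignore study site, although severe TRAE is now a facility-use outcome and the site mix of the controls is not stated

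*Combined protocol and SAP*

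**What the plan says.** **Outcome.** Protocol 7.5: "Severe TRAEs are defined as those requiring treatment in the hospital, ED, or Oncology Evaluation Center (OEC"). SAP items 26 and 27.2c use the same definition. The amendment history dates the change from Grade 3 or higher toxicity to version 6.0, May 2024.

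**Cohort contrasts.** SAP item 27.2c compares severe TRAE between prospective and historical carriers by chi-square, separately for DPYD variant carriers and UGT1A1 poor metabolizers. Item 27.2d does the same for relative dose intensity (RDI) by t-test. Neither is adjusted for anything.

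**Adjusted models.** Item 27.2c also plans a stepwise "multivariable logistic regression model adjusting for age, sex, race, tumor type, ECOG score, presence of metastases, intent of treatment, DPYD phenotype, and UGT1A1 phenotype", to look for factors that contribute to a TRAE. The list has no site term and no prospective-versus-historical term. The protocol's RDI, patient-reported outcome and Cox models (8.2.2, 8.2.3) list covariates without site, and its cost models list none.

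**Site.** Protocol 4.1 has the programme "deployed across cancer care sites within Penn medicine in sequential fashion, starting with PCAM followed by PPMC, and LGH". SAP item 27.1 uses site once, for result return: "The proportions were compared among clinical sites using a chi-square test". Protocol 5.4 gives annual gastrointestinal cancer volume of about 1000, 150 and 200 cases at PCAM, PPMC and LGH, and Table 4 there plans accrual of 240, 120 and 240. For the PMBB controls the documents give no site mix, restriction or matching.

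**The concern.** An outcome defined by where a patient was treated depends on toxicity, but can also depend on which facilities a site has and how readily it sends patients to them. The documents do not say which sites have an Oncology Evaluation Center. If the PMBB controls are spread over sites differently from the trial patients, and acute-care use differs by site, part of the difference between cohorts is a difference in care pathway. It would be read as an effect of genotype-guided dosing. The unadjusted tests cannot separate the two. Nor can the logistic model, which does not estimate the cohort contrast at all.

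At stake is the protocol's main effectiveness claim, a fall in severe TRAE among carriers.

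**Working it through.** **1. The plan's own figure.** Protocol 8.1 computes power "based on two-sided Fisher's exact test at the alpha level of 0.05". The severe TRAE rate "will decrease from 60% in the variant carriers receiving full dose chemotherapy in the historical control group" "to 30% in variant carriers receiving genotype guided chemotherapy". Carrier numbers rest on the statement that "testing 500 patients in each group will result in ~50 patients with actionable genotypes", and Table 5 gives 48 per group for 80% power. Exact enumeration of the two-sided Fisher test at 60% against 30% with n = 48 gives 80.0%. All 14 filled cells of Table 5 reproduce within 1 point. The SAP's chi-square test (no continuity correction) has 85.4% power on the same inputs. The point therefore does not rest on an error in Table 5.

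**2. Site mixes from the documents.**
- Planned accrual: 240/600, 120/600, 240/600 = 40/20/40%, so the share outside PCAM is 0.60.
- Clinic volume: 1000/1350, 150/1350, 200/1350 = 74/11/15%, so the share outside PCAM is 350/1350 = 0.259.

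**3. Spurious difference with no PGx effect.** Let d be the gap in acute-care use between PCAM and the other two sites, and s the share of controls outside PCAM. Then

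bias = (0.60 - s) × d.

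The documents give no acute-care rate by site, so d = 10 and 20 points is an assumption.
- Controls follow clinic volume: (0.60 - 0.259) × d = 0.341d, or 3.4 and 6.8 points.
- All controls from PCAM: 0.60d, or 6 and 12 points.
- Controls match the trial: 0.

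**4. Rejection rate of the crude test.** For n = 48 per group, sum Bin(a; 48, pH) × Bin(b; 48, pP) over all (a, b) for which the chi-square test rejects at two-sided 0.05. Here pH and pP are the site-weighted control and prospective rates, with the PCAM rate set at 60% or 40% and the other sites d lower.

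| Control site mix | Gap d | Spurious difference | Rejection, PCAM 60% | Rejection, PCAM 40% |
|---|---|---|---|---|
| Same as trial | 10 or 20 | 0 | about 5% | about 5% |
| Clinic volume | 10 | 3.4 | 6.4% | 6.4% |
| Clinic volume | 20 | 6.8 | 10.5% | 11.4% |
| PCAM only | 10 | 6 | 9.2% | 9.3% |
| PCAM only | 20 | 12 | 22.2% | 23.9% |

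Fisher's test, which the protocol names, is conservative. With a 60% PCAM rate it rejects 2.9% of the time with no site gap, 4.0% and 7.1% with volume-mix controls, and 6.0% and 16.5% with PCAM-only controls. If acute-care use is higher outside PCAM, the bias has the same size and the opposite sign.

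**5. What stratification does.** In 200,000 simulated trials per scenario, a Cochran-Mantel-Haenszel (CMH) test stratified by site rejects about 5.0% of the time under every control mix and gap above. Its power for 60% against 30% is 84% with matching mixes, 79% with volume-mix controls and 61% with PCAM-only controls, against 85% crude. The last figure is low because only the PCAM stratum then informs the contrast: about 0.40 × 48 = 19 prospective carriers against 48 controls.

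**The case against.** The strongest objection is that the size is assumed. No passage shows that acute-care use differs by site, so a 10-20 point gap has no documentary anchor. The largest rejection rates need PCAM-only controls and a 20-point gap together. With controls that follow clinic volume, the spurious difference is 3.4-6.8 points, against a planned effect of 30. The 40/20/40 mix is anticipated accrual, not actual enrolment. Table 5 pools the two genes while the SAP tests them separately, so each contrast may have fewer carriers. At an illustrative 25 per group, the 12-point case from a 40% control rate rejects 16% of the time by chi-square and 9% by Fisher. All of this stands.

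It is also fair that the historical contrasts are unadjusted for every covariate, that nothing in the documents ranks site above stage, ECOG status or calendar time, and that TRAE is secondary to feasibility. Site does have a specific reason to be handled: the outcome is defined by facility use.

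Four stronger readings are tempting, and the documents do not support them.
- *Site is a known source of variation in TRAE.* The SAP compares sites only on result return and turnaround.
- *The logistic model is where the PGx effect is confounded, and a site term there would cure it.* It has no cohort term.
- *Sequential opening itself biases the historical contrast.* It acts only through site mix and calendar time, and Table 4 starts PPMC and LGH in the same quarter.
- *Carrier versus wild-type comparisons within the trial are confounded by site.* That holds only if carrier frequency differs by site.

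**Conclusion.** The concern holds in conditional form. Three things are documented: no effectiveness analysis accounts for site, severe TRAE is defined by facility use, and the site mix of the controls is unstated. Bias then requires both a difference in site mix and a difference in acute-care use between sites. The documents establish neither, and they do not let a reader rule either out. Their own volume and accrual figures show that a mismatch is plausible.

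Under the assumed gap, the spurious difference runs from 0 (matching mixes) to 12 points (PCAM-only controls), and chi-square rejection under no effect from about 5% to about 24%. The direction is unknown. A reader might infer that the historical comparison is biased in favour of PGx; the documents support only that it could be biased, either way. This should be dealt with before the TRAE contrast is used as evidence of effectiveness. It does not touch the feasibility outcome.

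**What to change.** 1. Tabulate the PMBB controls by site, overall and among carriers, before any other step.
2. Beside each crude carrier-only contrast for TRAE and RDI, report a site-stratified estimate (for TRAE, CMH) or a site-adjusted one.
3. Add a sensitivity analysis restricted to sites present in both cohorts.
4. Add site to the item 27.2c logistic model as a forced term, exempt from stepwise removal, and to any adjusted RDI, cost or survival model that is retained. The SAP has replaced or dropped most of these: RDI is by t-test, one-year survival is only reported, and item 27 contains no cost analysis. This step alone does not protect the cohort contrast.

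**Cost.** Site must already be held for trial patients, since item 27.1 uses it, but it has to be retrieved for controls. Precision falls little when site mixes overlap (79-84% power against 85%), and materially (about 61%) if controls come only from PCAM. In that case the shared-site analysis is the interpretable one, and the report should say that PPMC and LGH carriers have no historical comparators.

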8.2 Overview of statistical methods

Descriptive statistics (mean, SD, median, interquartile range, range, counts, and percentage) will be used to describe and compare (t-test or rank sum test for continuous variables and Fisher's exact test for categorical variables) baseline characteristics between the historical control group and PGx arms.

8.2.1 Implementation Endpoint(s):

- We will report the number and proportion of tests returned prior to the first dose of chemotherapy.
- We will report the proportion of dose modifications made in agreement with genotype-guided dosing recommendations at the first dose.
- The proportion of tests ordered compared to the number eligible for testing.

8.2.2 Secondary Endpoint(s):

1. Clinical endpoints

- a. The proportion of patients experiencing severe TRAEs will be compared in the PMBB historical control group vs. the PGx group using Fisher's exact test.

Subgroup analyses will be performed by tumor type.

- b. The relative dose intensity (RDI) will be calculated for 5-FU, capecitabine or irinotecan as the cumulative administered dose divided by the anticipated cumulative dose over the first 6 cycles. RDI will be compared in the PMBB historical control group vs. the PGx group using linear regression adjusted for sex, race, BMI, tumor type, cancer stage, line of therapy and ECOG performance status.

Subgroup analyses will be performed by tumor type.

2. Patient reported outcomes

Patient reported outcomes as assessed on a Likert scale will be reported as means (SD) and compared between the PMBB historical control group vs. the PGx group using linear regression adjusting for age, sex, race, tumor type, cancer stage, BMI, line of therapy, and ECOG performance status.

3. Patient attitudes toward PGx testing

Patient knowledge and attitudes towards PGx testing will be assessed on a Likert scale will be reported as means (SD). We will compare results by sex, race, tumor type, and insurance status by using linear regression. (See survey in Appendix 14.7)

8.2.3 Tertiary Endpoint(s):

1. Clinical endpoints in minority populations

The proportion of patients experiencing severe TRAEs will be compared in the PMBB historical control group vs. the PGx group using Fisher's exact tests, stratified by race.

2. Minor allele frequencies will be reported by ancestry for the DPYD and UGT1A1 genes.
3. Medical services utilization and costs

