We will obtain data from Data Analytics Center (DAC) on service utilization and costs. These will include: number of physician visits; number of emergency department visits; number of hospitalizations; length of hospital stay; number of emergency department and hospital admissions associated with drug-related adverse events; DPYD and UGT1A1

genetic testing costs; physician visit cost; emergency department visit costs; hospitalization costs; inpatient and physician-administered medication costs; and total costs. Care Everywhere will be utilized to obtain information if patients received care outside Penn Medicine. Additionally, medical records will be requested for admissions that occur outside of Penn Medicine.

We will compare utilization and costs incurred by the PMBB usual care group with utilization and costs incurred by the PGx group using Poisson regression methods (for number of visits), and linear regression methods with appropriate transformations (e.g., log-transform, winsorization) to account for skewness in utilization and cost distributions.

4. Survival Analysis

Overall survival and progression free survival at approximately six months will be compared between the PMBB historical control group vs. the PGx group by use of Kaplan-Meier estimators and log-rank tests. Cox proportional regression analysis will be performed to adjust for clinical covariates including age, sex, race, tumor type, cancer stage, BMI, and ECOG performance status.

5. Pre-treatment uracil and fluoropyrimidine associated toxicity

First, we will examine the range of pre-treatment uracil concentrations with the association of severe toxicity to determine if there is a cut-off whereby toxicity occurs. Previous studies have proposed uracil $> 16\text{g/ml}$ as highly predictive for severe toxicity, but we will validate this cut-off in our patient population.¹⁵ We will also examine whether the pre-treatment uracil levels vary in *DPYD* variant carriers. Second, we use logistic regression models to determine the risk of severe toxicity including a binary factor for uracil concentration (above and below cut-off), with adjustment for age, sex and treatment regimen.

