		5. To determine if providing PGx test results will improve patient reported outcomes (PRO) during the first six cycles of chemotherapy.
Hypothesis	9	Providing clinicians with the ability to order a PGx test with a rapid turnaround time for results, along with specific dosing recommendations, will increase the utilization of PGx tests to guide pharmacotherapy decisions and improve patient drug related outcomes.

Section 3: Study Methods

Section	Index	Description
Trial design	10	Non-randomized, prospective, open-label implementation study to determine the feasibility of establishing and integrating a PGx test into clinical care.
Randomization	11	n/a
Sample size	12	No sample size calculation was performed for this feasibility study with pragmatic inclusion of eligible participants recruited over a 20- month period (Mar 2021- Dec 2022).
Interim analyses	13	No interim analyses planned
Timing of final analysis	14	Participants were followed until May 31, 2023, for toxicity assessments with an intention of 6-month follow-up for each participant. All analyses were performed collectively in May-June of 2024.
Timing of outcome assessments	15	Serial questionnaires assessing patient reported outcomes (PROs) for symptoms associated with to adverse events will be prospectively collected by the study team at the time of each treatment for the first 6 cycles.

Section 4: Statistical Principles

Section	Index	Description
Confidence intervals and p-value	16	
No hypothesis testing was performed for the primary outcome (feasibility) or secondary implementation outcomes (fidelity, penetrance).
 
Descriptive statistics (mean, SD, median, interquartile range, range, counts, and percentage) will be used to describe and compare (t-test or rank sum test for continuous variables and Fisher's exact test for categorical variables) baseline characteristics between the historical control group and PGx arms.
 
For the effectiveness aims, significance was set at an alpha=0.05.
 
No corrections were made for multiple testing. Confidence intervals pertaining to the odds of experiencing a severe TRAE were reported.

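### The SAP's only adjusted severe-TRAE model uses an undefined stepwise method with neither phenotype forced in, so the adjusted DPYD and UGT1A1 odds ratios may be dropped or, for weak to moderate effects, overstated

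*Combined protocol and SAP*

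**What the plan says.** SAP Section 6, item 27.2c, first compares severe TRAE by genotype within the prospective cohort, and between the prospective and historical cohorts within genotype. These comparisons are unadjusted: "Chi-square tests were used for all comparisons".

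It then adds one adjusted analysis: "Factors contributing to having a TRAE were evaluated using a multivariable logistic regression model adjusting for age, sex, race, tumor type, ECOG score", and the list continues "presence of metastases, intent of treatment, DPYD phenotype, and UGT1A1 phenotype using a stepwise approach". That makes nine factors, two of them the study phenotypes. The item does not say whether selection is forward, backward or both, what criterion governs entry or removal, whether any term is forced in, or which cohort the model is fitted to. It lists no cohort term.

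SAP Section 4, item 16, adds: "Confidence intervals pertaining to the odds of experiencing a severe TRAE were reported". It also says "For the effectiveness aims, significance was set at an alpha=0.05" and "No corrections were made for multiple testing". No bootstrap, shrinkage or post-selection interval is mentioned.

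Protocol 8.2.2 plans no adjusted severe-TRAE comparison. The proportions "will be compared in the PMBB historical control group vs. the PGx group using Fisher's exact test". The protocol's one other adjusted model of severe toxicity is the tertiary uracil analysis in 8.2.3 ("we use logistic regression models to determine the risk of severe toxicity including a binary factor for uracil concentration"), which has no genotype or cohort term.

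**The concern.** Carriers and wild-type patients are not randomised groups. The multivariable model is therefore the SAP's only means of asking whether a toxicity difference by phenotype reflects case mix. A stepwise search lets the data decide whether the phenotype terms, and the covariates meant to adjust them, stay in.

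Two results follow. A phenotype with a real but modest effect will often be removed, leaving no adjusted estimate. When it survives, it has done so partly because its estimate happened to be large, so the reported OR tends to sit too far from 1 and the usual interval ignores the selection that produced it. Because the rule is not stated, a reader can neither reproduce the selection nor judge how strong these effects are.

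**Working it through.** **1. The plan's own figure.** The only severe-TRAE calculation in the documents is protocol Table 5: two-sided Fisher's exact test, 60% against 30%, 48 carriers per group, power 80%. Full enumeration gives 80.0%, and all 14 filled cells agree within 2 percentage points. That table concerns an unadjusted cohort comparison. Neither document gives an operating characteristic for the stepwise model, so the rest rests on stated assumptions.

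**2. Carrier frequency.** The DPYD allele frequencies in protocol Table 1 sum to 0.0372 (European ancestry) and 0.021 (African ancestry), with unreported entries taken as zero. Protocol 5.4 puts African ancestry at about 20%; the remainder is treated as European. Carrier share ≈ 0.8 × 2 × 0.0372 + 0.2 × 2 × 0.021 = 0.0595 + 0.0084 = 6.8%.

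**3. Which effect sizes matter.**
- 60% against 30% is an OR of (0.60/0.40)/(0.30/0.70) = 3.5. It contrasts historical with guided carriers, and the model has no cohort term.
- The 2019 single-center study cited in protocol 2.2 gives 37.9% in dose-reduced carriers against 27.3% in wild-type patients: (0.379/0.621)/(0.273/0.727) = 1.63.
- The planned 30% in guided carriers, set against up to 30% severe fluoropyrimidine toxicity in general (protocol 2.2), suggests an OR near 1.

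If the model is fitted to the prospective cohort, weak to moderate effects are therefore the relevant range. These sources may not define toxicity as the SAP does, so this is indicative only.

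**4. Hand check of the selection effect.** Assume 37% TRAE in wild-type patients, a true OR of 1.5 (so 46.8% in carriers), and a term kept only at p<0.05.
- SE² = 1/[n_c p_c(1−p_c)] + 1/[n_w p_w(1−p_w)]
- c = 1.96 − ln(OR)/SE
- P(kept) ≈ P(Z>c)
- mean retained log OR = ln(OR) + SE·φ(c)/P(Z>c)
- coverage when kept = P(c<Z<1.96)/P(Z>c)

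N=450 (30.6 carriers):
- SE² = 1/7.62 + 1/97.8 = 0.1415, so SE = 0.376
- c = 1.96 − 0.405/0.376 = 0.882
- P(kept) = 0.19
- retained OR = exp(0.405 + 0.376 × 0.270/0.189) = 2.57
- coverage = (0.189 − 0.025)/0.189 = 87%

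N=800 (54.4 carriers):
- SE = 0.282, c = 0.523
- P(kept) = 0.30
- retained OR = exp(0.405 + 0.282 × 0.348/0.3005) = 2.08
- coverage = (0.3005 − 0.025)/0.3005 = 92%

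**5. Simulation of the model.** Backward elimination was used as one form of stepwise selection, with modest assumed covariate effects.

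With 6.8% carriers, a stay criterion of p=0.05 and N from 450 to 800:
- True DPYD OR 1.5: kept in 19% to 28% of trials, retained OR 2.7 to 2.1, coverage 83% to 92%.
- True DPYD OR 3.5: retained OR 4.0 to 3.6, coverage 97% to 98%.
- Full model: coverage 94% to 96%.

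With N=500, 5% DPYD carriers, 10% UGT1A1 poor metabolizers, baseline TRAE about 30% and 1,500 runs per scenario (median OR when kept):

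| Term, stay p | True OR | Kept | OR when kept | Coverage when kept |
|---|---|---|---|---|
| DPYD, 0.05 | 1.5 | 15.5% | 2.81 | 84% |
| DPYD, 0.05 | 2.0 | 38.5% | 2.99 | 94% |
| DPYD, 0.05 | 3.5 | 82.9% | 3.91 | 97% |
| UGT1A1, 0.05 | 1.5 | 28.2% | 2.14 | 94% |
| UGT1A1, 0.05 | 2.0 | 61.9% | 2.33 | 96% |
| UGT1A1, 0.05 | 3.5 | 97.7% | 3.60 | 96% |
| DPYD, 0.157 | 1.5 | 33.1% | 2.31 | 88% |
| UGT1A1, 0.157 | 1.5 | 45.1% | 1.90 | 94% |

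In the same runs the full model gave median ORs of 1.48 to 1.54 at a true 1.5, 2.00 to 2.04 at 2.0 and 3.56 to 3.65 at 3.5, with 94% to 96% coverage.

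**6. Can the full model be fitted?** An assumed 30% of 500 gives 150 events. With 9 to 14 parameters, depending on how tumor type and race are coded, that is 150/14 = 11 to 150/9 = 17 events per parameter.

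**The case against.** The strongest reply is that the exaggeration is a significance filter, not something peculiar to stepwise selection. In one set of runs at N=450 and a true OR of 1.5, DPYD was retained about as often as it was significant in the full model (18.3% against 18.5%), and the significant full-model ORs were just as inflated (2.64 against 2.63). This is correct. It means that what protects the estimate is reporting both ORs regardless of significance, which a stepwise model with no forced terms does not ensure.

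Other parts of the reply also stand, and they rule out stronger readings that a reader might infer:
- **That a phenotype result appears only when significant.** The chi-square comparisons by DPYD carrier status and UGT1A1 poor-metabolizer status do not depend on the model. Only the adjusted estimate can be lost.
- **That the phenotypes were dropped.** The text permits this but does not state it; terms may have been forced in.
- **That the odds ratios and intervals are simply invalid.** Coverage is close to nominal in many scenarios, and the bias shrinks with a larger sample, a stronger effect or a looser rule. At N=800 with a 0.157 rule and a true OR of 1.5, the retained OR was 1.89 with 94% coverage. The 0% coverage found at a true OR of 1 under the 0.05 rule is nearly automatic, since a term kept only at p<0.05 has an interval that excludes 1.
- **That item 16's intervals all come from this model.** Item 16 does not name their source, although the logistic model is the natural one.
- **That metastases and treatment intent are nearly the same variable.** This is plausible, but nothing in the documents shows it.

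**Conclusion.** The concern holds in limited form. The SAP's only adjusted severe-TRAE model leaves both phenotype estimates to an unstated selection rule. For a true DPYD OR of 1.5 under a 0.05 rule, this means no adjusted estimate in roughly 72% to 81% of trials at N from 800 down to 450. When the term is kept, the OR is about 2.1 to 2.7, with 83% to 92% coverage. For an OR of 3.5 the effect is minor.

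These sizes depend on assumptions not in the documents: backward elimination, the stay criterion, the event rate, the covariate effects and the true ORs. The direction of the problem does not depend on the exact values chosen; its size does.

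A reader might infer that the trial's main conclusions are at risk. The documents do not support that. The primary outcome is feasibility and is untouched, and with no cohort term listed the model does not estimate the guided-against-historical contrast. This is a secondary explanatory model that should be fixed, not a critical flaw.

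**What to change.** In item 27.2c, make the main adjusted analysis one logistic model with all nine listed factors retained and both phenotypes forced in. Name the cohort it is fitted to. Report the DPYD and UGT1A1 ORs with 95% CIs whatever their p-values.

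Settle the estimation method before the re-run, for example Firth's penalised likelihood because carriers are few. Do not switch to it, or drop metastases or intent, after seeing the data.

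Item 14 describes the analyses as already performed in May-June 2024, so record the change as a dated revision and do not erase the stepwise wording. If the stepwise result is kept, state its direction and its entry and stay criteria, and label it exploratory.

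The cost is a short SAP revision and a re-run on existing data, with slightly wider intervals. No new data are needed.
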